C.2.6. Neurosteroid Analyses: To compare ALLO results with Sripada et al.'s 2013, basal serum levels will also be taken (once prior to drug administration and once two hours after oral administration of the drug study) and analyzed using a gold-standard in the literature: a gas-chromatographic mass-spectrometric (GC-MS) approach. Serum levels of pregnenolone, progesterone, 5alpha-DHP and ALLO and pregnanolone (ALLO's steroisomer and GABA-active) will be measured. As in Majewaska et al (2014), saliva samples will be analyzed using the same gold standard GC-MS approach in ALLO literature i.e., a method that allow for accurate measurement in the femtomolar range of specific neurosteroids. We will ensure that participants will refrain from smoking, eating, drinking alcoholic, caffeinated, or juicy beverages, and brushing teeth at least one hour before the first saliva sample and between saliva samples.

C.2.7. General Statistical approach:

Demographic and self-report psychological measures: Statistical analyses for demographic and self-report measures will be computed using SPSS software. Prior to inferential analyses, descriptive statistics, including distributions, means, standard deviations, skewness, and kurtosis will be generated. Data will also be examined for the pattern and mechanism of missing data. Continuous data will be tested for normality and homogeneity of variance. Potential differences between the study groups in terms of demographic and behavioral measures will be explored using multivariate analysis of variance (MANOVA) or appropriate non-parametric tests as appropriate. The overall significance level for these analyses will be at 5% using two-tailed tests and effect sizes and confidence intervals will be reported. In addition, scores at self-report questionnaires will be analyzed via a 2 (Drug Type: PREG 400mg, or PBO) x 2 (time: before, after) repeated measures ANOVA to assess for main effects and interaction effects.

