Behavioral paradigms: Statistical analyses will be computed using SPSS software. Reaction times and performance data will be screened and any outliers will be removed based on each participant's trial-by-trial data. A trial will be removed if it differed by 3 standard deviations above or below the participant's mean. Prior to inferential analyses, descriptive statistics, including distributions, means, standard deviations, skewness, and kurtosis will be generated. Data will also be examined for the pattern and mechanism of missing data.

• For the *body language* paradigm: A 2 (Drug Type: PREG 400mg, or PBO) x 2 (type of stimuli: social, non-social) x 2 (nature of the stimuli: threat, non-threat) repeatedmeasures ANOVA will be performed on the reaction times and valence ratings to assess for main effects and interaction effects. P values, confidence interval, and effect sizes will be reported.

C.2.6. Power Analysis: Using G* power calculation software (Version 3.1.9.2; © Franz Faul, Edgar Erdfelder, Albert-Georg Lang, and Axel Buchner, 2006, 2009) for a within-between interaction in a repeated measures ANOVA, a total sample size of 36 for three groups will yield 95% power to detect a significant difference, with alpha = 0.05 and an effect size Cohen's *d of* 0.35 in the present project.

Note: The hormone tested in saliva and blood have the same origin from adrenals glands and gonads. Here we want to establish a correlation within the same subjects among the levels of the same neuro-active steroid determined in the blood and the saliva. We expect the hormone levels measured in saliva and in blood to be different in amount but to correlate.

Saliva samples will be analyzed using the same gold standard GC-MS approach in ALLO literature i.e., a method that allow for accurate measurement in the femtomolar range of specific neurosteroids. We will ensure that participants will refrain from smoking, eating, drinking alcoholic, caffeinated, or juicy beverages, and brushing teeth before each saliva sample.

7. Special Precautions:

Pregnenolone side effects, danger, risk, and the harm it can cause

Overstimulation and insomnia -

Irritability, anger or anxiety -

Acne can occur due to the probable conversion of this hormone into androgens

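### The 95% power stated for a Cohen's d of 0.35 appears to have been calculated with Cohen's f = 0.35; a d of 0.35 does not give 95% at N = 36 without an unstated, very high before-after correlation

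*Combined protocol and SAP*

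**What the plan says.** The only power statement is in section 7 (Research Methods), under C.2.6 Power Analysis. It says that "for a within-between interaction in a repeated measures ANOVA, a total sample size of 36 for three groups will yield 95% power", "with alpha = 0.05" and an "effect size Cohen's *d of* 0.35 in the present project". The paragraph does not give the number of repeated measurements, the correlation between them, or the scale on which d is defined.

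The number of time points has to be taken from C.2.7 General Statistical approach, where questionnaire scores are analysed by a "2 (Drug Type: PREG 400mg, or PBO) x 2 (time: before, after) repeated measures ANOVA". The Approach (section 7) and section 8 give the current sample as 224 randomised men, 112 per arm, plus 12 matched healthy controls (MHC) who receive no study drug. Section 9 still gives a total of 36.

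**The concern.** Cohen's d compares two means. A three-group interaction is tested by an omnibus F test, whose effect size has to summarise the spread of all the group means, and that is Cohen's f. The two are on different scales, so 0.35 as f is a much larger effect than 0.35 as d.

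This is the plan's only planning effect size. If the label is wrong, readers will take the trial to have been sized for a small-to-moderate effect with 95% power when the calculation covers a far larger one. The error is also separate from the mismatch between 36 and 224 subjects. If only the sample size were corrected, the pairing of d = 0.35 with 95% could be carried into the new sentence, where it would look plausible.

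**Working it through.** **Inputs.** From Power Analysis: N = 36, k = 3 groups, alpha = 0.05, effect size 0.35, claimed power 95%. From C.2.7: m = 2 time points. From The Approach: 112 per randomised arm. Assumed, because the documents give no value: before-after correlation rho = 0.5, varied below.

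**Formula.** Noncentral F for the group-by-time interaction: lambda = f² × N × m / (1 − rho), df1 = (k − 1)(m − 1), df2 = (N − k)(m − 1).

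**1. The plan's figure, with 0.35 as f.**
- N = 36: lambda = 0.1225 × 36 × 2 / 0.5 = 17.64, df 2 and 33, power 95.7%.
- N = 33: lambda = 16.17, df 2 and 30, power 93.8%.

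So 36 is the smallest equal-group total that reaches 95%, which is the plan's figure. At N = 36 the result for other correlations is 86.8% (rho 0.3) and 99.8% (rho 0.7).

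**2. The same test, with 0.35 as d (N = 36, rho = 0.5).**

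| Reading of d = 0.35 | f | Power | rho needed for 95% |
|---|---|---|---|
| Simple conversion, f = d/2 | 0.175 | 41.8% | about 0.87 |
| Difference in change, two-group conversion d/4 | 0.0875 | 13.3% | about 0.97 |
| Difference in change, one group apart from two equal groups | 0.0825 | 12.3% | about 0.97 |
| Difference in change, three evenly spaced groups | 0.0714 | 10.4% | about 0.98 |

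**3. What f = 0.35 means as a difference in change.** With two time points, f is the SD of the group mean changes divided by 2 × the raw SD. Let D be the largest between-group difference in change, in raw SDs.
- Two groups: f = D/4, so D = 4 × 0.35 = 1.40.
- Three groups, one apart from two equal: f = D√2/6, so D = 0.35 × 6/√2 = 1.48.
- Three groups evenly spaced: f = D/(2√6), so D = 0.35 × 2√6 = 1.71.

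Relative to 0.35 these are 4.0, 4.2 and 4.9 times. On the simple scale (d = 2f for two groups) the values are half as large and the multiples are 2.0 to 2.4.

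For three groups, D is the largest difference between any two groups and need not be PREG against PBO. At f = 0.35 the PREG-PBO difference is 0 if only the MHC group differs, and 1.71/2 = 0.86 SD if PBO lies midway between PREG and MHC.

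**4. d = 0.35 at the current randomised sample (112 per arm).** Two-sided two-sample noncentral t, with d the PREG-PBO difference in change in raw SDs. The SD of change is SD × √(2(1 − rho)); with the pre-dose score as covariate it is SD × √(1 − rho²). At rho = 0.5 on change scores, the noncentrality is 0.35/√(2/112) = 2.62.

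| Assumed rho | Change score | Pre-dose score as covariate |
|---|---|---|
| 0.3 | 60% | 78% |
| 0.5 | 74% | 85% |
| 0.7 | 92% | 95% |
| 0.8 | 98% | 99% |

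Power of 95% needs rho of at least about 0.74 on change scores, or about 0.69 with the covariate.

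**The case against.** The strongest reply is that the use of f is inferred. The paragraph states neither m nor rho, and the match at 36 needs m = 2 and rho = 0.5. Other parts of the plan have more measurements: blood and saliva are taken three times, and the body-language ANOVA has four within-subject cells. With f = 0.35 and rho = 0.5, power at N = 36 would be 98.8% for three measurements and 99.7% for four. Other definitions of the interaction effect size give 38.7% or 41.8% for 0.35 entered as f. This stands, and it is why the point says that the figure appears to come from f. It does not rescue the sentence: at two time points, a d of 0.35 reaches 95% only with a correlation that the plan neither states nor justifies.

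A second reply is that questionnaires repeated within one visit may correlate above 0.8. That is possible; at rho = 0.87, a d of 0.35 on change scores has 99.9% power at 112 per arm. The documents give no value, so this is a reason to state and justify one.

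A third reply is that the planned randomised sample is 224, so a 36-subject paragraph no longer governs the trial. A new two-arm calculation would indeed replace the sentence. But it remains the plan's only power statement, and changing N alone would leave the wrong metric in place.

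**Conclusion.** The power statement is wrong as written. With two time points and rho = 0.5, the stated N and power fit f = 0.35 (95.7%) and do not fit d = 0.35 (about 42%, or 10% to 13% on the difference-in-change scale). The conclusion rests on m = 2, taken from the questionnaire model, and on the assumed correlation.

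A reader might infer three stronger things that the documents do not support:
- **That 0.35 was certainly entered as f.** The inputs are not recorded, so this remains an inference, though a strong one.
- **That the calculation covers only a PREG-PBO difference at least four times the stated one.** A three-group omnibus f does not fix the PREG-PBO contrast. The 1.48 to 1.71 SD is a largest between-group difference, and the multiple depends on the scale (2.0 to 2.4 on the simple one).
- **That the trial of 224 is underpowered for d = 0.35.** Power there runs from 60% to 99% over assumed correlations of 0.3 to 0.8. What can be said is that 95% is not supported until a correlation is justified.

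**What to change.** Replace the Power Analysis sentence with a power statement for the randomised two-arm Drug x time contrast at 112 per arm. It should name the effect-size metric and its scale (for example, the PREG-PBO difference in pre-post change in raw SDs), the number of measurements, the assumed before-after correlation with its justification, and whether the pre-dose score is a covariate. The last table above gives the power to quote for d = 0.35. Claim 95% at that effect only if a correlation of at least about 0.74, or about 0.69 with the covariate, is justified.

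If the existing calculation is kept as a record, label it Cohen's f = 0.35 for the three-group omnibus interaction at N = 36, state m and rho, and do not translate it into a PREG-PBO difference.

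The cost is one rewritten paragraph, with no extra participants and no change to conduct. The stated power becomes less favourable unless a high correlation can be supported.

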
Rationale for selected dose range in the present project: Here, 224 subjects high in PSI will be randomized to a single oral dose of PREG 400mg (n=112), or placebo (PBO, n=112) to ascertain dose of administration. The rationale for the selected dose range is the following: First, clinical trials showed that PREG 25–500 mg/day is safe and well tolerated in humans. Second, Sripada and colleagues made the compelling basic science discovery that a single dose (400mg) of PREG up-regulates ALLO in young adults (See Fig. 1) and reduces activation of brain areas underlying negative emotions processing.

Steroid (pg/ml)	Placebo (n=15)		Pregnenolone Group (n=16)			
	Baseline (Mean ± SD)	Endpoint (Mean ± SD)	Baseline (Mean ± SD)	Endpoint (Mean ± SD)	ï	р
Pregnenolone	1378.8 ± 579.1	1190.8 ± 468.5	1238.0 ± 378.7	3943.6 ± 696.3	12.3	<.001
Allopregnanolone	114.3 ± 49.6	118.1 ± 76.5	112.3 ± 40.9	802.2 ± 280.7	10.2	<.001
Pregnanolone	470.6 ± 200.8	490.5 ± 135.6	352.0 ± 106.6	517.4 ± 96.2	3.2	.004

Fig. 1. Steroid and metabolite levels in Sripada et al.'s 2013. *T-tests were conducted on change scores (steroid levels at endpoint minus steroid levels at baseline). Pregnenolone group received an acute, oral dose of PREG 400mg.

Based on pharmacokinetic data in humans, we expect the peak serum concentration of ALLO to occur approximately 2 hours after acute, oral administration of PREG 400mg. Saliva levels will be measured at the following 3 time points: -0.5, 2.0, 3.0 to provide various measures and correlations with behavioral tasks and correlations with serum levels.

4. Aims & Hypotheses:

Specific Aim 1: Assess PREG on levels of ALLO in a dose-finding design. Relative to PBO, PREG will dose-dependently increase and normalize ALLO levels in individuals high in PSI such that it will be comparable to Matched Healthy Controls (MHC) (Hypothesis 1A).

Specific Aim 2: Examine PREG on attentional bias to social threats and depressive symptomatology in individuals who are high in PSI. Relative to PBO, PREG will reduce depressive symptomatology and attentional bias to social threats and improve intention understanding and perception of others in individuals high in PSI (Hypothesis 2A). Hypothesis 2B: In PSI and MHC, depressive symptomatology and attention to social threats will correlate negatively with ALLO levels.

5. Duration of the study: The total duration of the entire study on campus is between 4 and 4 $\frac{1}{2}$ hours maximum.

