7. RESEARCH METHODS

The Approach

This project will comprise a randomized, placebo- controlled, between-subjects design, where we will couple a validated behavioral paradigm on attention to social threats with an acute pharmacological challenge with oral pregnenolone (PREG) or placebo (PBO) in subjects high in PSI and test behavioral responses and neuro-active steroid levels *prior and after study oral drug administration*. In the present project, 224 PSI subjects will be randomized to a single oral dose of PREG 400mg (n=112), or placebo (PBO, n=112) to ascertain dose of administration. In this project, participants will attend a single laboratory visit. During this single session, behavioral responses and subjective feelings will be tested at two time points (once before and once after). Neuro-active steroids will be measured from blood and saliva at several points to ascertain they correlate. A group of Matched Healthy Controls (MHC) who are low in PSI (n=12) and will not receive PREG but will otherwise complete all questionnaires of the study. Participants will be recruited from the University of Chicago and in the community.

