can see how his blood hormones change at different times. The experimenter will draw blood from the subject's arm three times: 1) 30 minutes after your arrival at the high-performance electrical neuroimaging laboratory, 2) one 2 and 30mn later and 3) again an hour later. About 1 teaspoon of blood will be taken each time.

- The subject will also be asked to provide saliva samples during the study at the same three times: 1) 30 mn after your arrival at the high-performance electrical neuroimaging laboratory, 2) one 2 and 30mn later and 3) again one an hour later. About 1 teaspoon of saliva will be taken each time. We ask the subject to provide saliva samples so that we can see how the samples are related to behavioral tasks and how the subject is feeling at different times in the study.
- The subject will watch a 2-hour-long relaxing movie in a quiet and relaxing environment.

Two hours after the subject takes the pill (drug or placebo), the following will occur:

- The subject will do the exact same behavioral visual task on a computer . Control subjects will perform the same tasks at the same time, except they will not take any pills.
- The subject will complete the same questionnaires again.
- The subject will wait for 30 minutes in a relaxing and quiet environment.
- The subject will be given a parking voucher or \$5 for public transportation and a \$60 monetary compensation for participating in the study.

Estimated Duration of Visit: Between 4 Hours and 4 ½ hours

In the event suicidal ideation or similar events take place during the study, the subject will be removed from the study and referred to the appropriate clinical resources.

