A researcher will be present with participants during the duration of the experiment. While participants are in a separate room sheltered, researchers will monitor participants' wellbeing via cameras and microphones within this room. Participants will have the ability to communicate with researchers through these microphones and may opt out of participation at any time. Participants will also be provided with the IRB's contact information on the consent form, and we will contact IRB should any adverse effects occur.

Regarding pregnenolone's side effects: Subjects will be directed to call a member of the study team if they believe they are experiencing any side effects within the 12 hours following the end of the study.

13. Payment:

Participants will receive the \$60 monetary compensation (Internal Fundings/No Fund) for their participation in the entire study. If participants should decide to opt out of participation after the beginning of the study, their participation would be pro-rated (\$15 per hour).

14. Informed Consent:

We are asking to waive first consent form to do a brief phone interview and see whether the participants are eligible. Then the participants will come to the University of Chicago and read, understand and sign the written consent form attached in this IRB application. Participants must acknowledge understanding of procedures, risks, and benefits by signing this consent form before the study can proceed.

15. Confidentiality:

De-identified data will be stored in locked drawers or cabinets or on password-protected computers within the HPEN laboratory or on password protected University of Chicago server, such as UChicago Box. Data may be used in publications, but no personally identifiable information will be disseminated outside of researchers included in this protocol.

16. Recruiting Methods:

Subjects will be recruited via Flyers posted on Campus, sona or websites, such as craigslist.

17. Primary Physician Notification:

[name], M.D.

18. Anticipated Coordination between Inter-Departmental Faculty:

[name]., [name]., and [name]. are all members of the Department of Psychiatry and Behavioral Neuroscience. [name] is the Director of the Center for Cognitive and Social Neuroscience. These researchers will coordinate extensively on this project.

19. Pregnancy Test: N/A. The present research only includes male participants.

20. Drug Test:

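### After the visit, side effects are learned of only through an unsolicited call tied to an ambiguous 12-hour window, so insomnia, a named risk, is likely to be under-counted, and unevenly by visit start time

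*Combined protocol and SAP*

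**What the plan says.** Section 7 (Research Methods) states that "participants will attend a single laboratory visit". Its length is given as "Estimated Duration of Visit: Between 4 Hours and 4 ½ hours". The last step before payment is a rest period: "The subject will wait for 30 minutes in a relaxing and quiet environment". No later contact is scheduled.

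Section 12 (Monitoring of Safety) covers two periods. During the visit, a researcher is present, participants are watched by camera and can speak to staff by microphone, and the IRB is to be contacted if adverse effects occur. After the visit, men are told to call the study team "if they believe they are experiencing any side effects within the 12 hours following the end of the study".

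The Special Precautions section begins its list of pregnenolone's side effects with "Overstimulation and insomnia". It goes on to name irritability, anger or anxiety, headache, and palpitations or heart-rhythm irregularities, among others.

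The statistical sections (C.2.7 and the behavioural and power paragraphs after it) describe no side-effect analysis by arm. Sections C.2.3 and C.2.4 list the instruments but name no side-effect checklist or sleep measure.

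**The concern.** Insomnia shows itself at night. The visit is over by then, and what remains is a call that the man must decide to make. Two features of that call weaken it as a source of safety data.

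First, the 12 hours run from the end of the visit and not to a fixed point such as the next morning. How much of the first night is covered therefore depends on when the man was booked.

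Second, the call is unsolicited and depends on the man's belief that he has a side effect. Men who guess that they received active drug may call more readily. Participants are blinded, so this is a possibility and not a demonstrated bias, but asking everyone the same question would guard against it.

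At stake is whether few or no calls could be taken as evidence of good tolerability. That matters beyond this study: Section 3 gives repeated daily use as the project's wider objective, and Section 4 relies on earlier trials for the view that side effects are minimal.

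**Working it through.** **Inputs from the documents**
- Visit length L: 4.0 to 4.5 h (Section 7, Research Methods).
- Blood and saliva sampling: "1) 30 minutes after your arrival at the high-performance electrical neuroimaging laboratory, 2) one 2 and 30mn later and 3) again an hour later" (same section). The second interval is read as 2 h 30 min.
- Saliva schedule: "Saliva levels will be measured at the following 3 time points: -0.5, 2.0, 3.0" (Section 4, dose-range rationale), taken as hours relative to the dose.
- Post-visit window: 12 h (Section 12).

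**Assumed, because the documents do not say:** start time, bedtime (23:00) and waking time (07:00, varied from 06:00 to 08:00).

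**Step 1. Reproduce the visit length.** 0.5 + 2.5 + 1.0 = 4.0 h to the last sample, which agrees with the stated 4 to 4.5 h. The intervals also match the saliva schedule: 2.0 − (−0.5) = 2.5 h and 3.0 − 2.0 = 1.0 h. The dose therefore falls about 0.5 + 0.5 = 1.0 h after arrival.

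**Step 2. Closing time.** Close = start + L + 12 h. Measured from the dose, this is L − 1.0 + 12 = 15.0 to 15.5 h.

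| Start | Visit ends | Window closes | Hours covered after a 23:00 bedtime (of 8) |
|---|---|---|---|
| 08:00 | 12:00–12:30 | 00:00–00:30 | 1.0–1.5 |
| 09:00 | 13:00–13:30 | 01:00–01:30 | 2.0–2.5 |
| 12:00 | 16:00–16:30 | 04:00–04:30 | 5.0–5.5 |
| 13:00 | 17:00–17:30 | 05:00–05:30 | 6.0–6.5 |
| 15:00 | 19:00–19:30 | 07:00–07:30 | 8.0 |

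**Step 3. Earliest start that covers the whole night.** Counting 07:00 next day as hour 31, start ≥ 31 − 12 − L. This gives 15:00 for L = 4.0 and 14:30 for L = 4.5.

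**Step 4. Share of visits affected, for illustration.** With starts spread evenly over 09:00–17:00 and waking at 07:00, the share closing before the night ends is (15.0 − 9)/8 = 75% for L = 4.0 and (14.5 − 9)/8 = 69% for L = 4.5. Moving waking to 06:00 or 08:00 widens the range: (13.5 − 9)/8 = 56% to (16.0 − 9)/8 = 88%. If all starts fall between 08:00 and 13:00, the share is 100%.

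**Step 5. Window that would be needed.** For an 08:00 start and waking at 07:00, cover would have to last 18.5 to 19 h after the visit ends, against 12 h.

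**Step 6. The two readings of the sentence.** If the 12 hours is a deadline for calling, a man starting at 09:00 must call by 01:00–01:30. If it limits when the effect is experienced, he may call next morning about failing to fall asleep, but sleep lost after 01:00–01:30 is still outside it. On both readings the report remains unsolicited.

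**The case against.** The strongest reply is that side effects do not depend on a phone call alone. A researcher, cameras and microphones cover the visit, and the sentence about contacting the IRB has no time limit. This stands for the visit itself: it would be wrong to infer that side effects are collected only by phone. It does not help with insomnia. Observation ends before the first night, and the IRB sentence governs events already known to staff without providing a way to find them.

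A reader might also infer that insomnia cannot be counted, or that every morning or midday visit misses it. The documents do not support that. On the assumed 23:00 bedtime, the window reaches past bedtime for every start from 08:00 on. A man who cannot fall asleep knows it at the time. On the occurrence reading, a next-morning call about slow sleep onset would also qualify.

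The questionnaires are repeated two hours after the pill, and the Hospital Anxiety and Depression Scale is among them, so anxiety is probably measured in both arms. The items are not printed, so it cannot be said that none concerns sleep. For insomnia this makes no difference, since no night has passed by then.

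Finally, the plan sets no tolerability endpoint and promises no tolerability conclusion, and the consent form mentioned in Section 14 was not available for this review and may carry further instructions. Both points stand. They limit the consequence but leave the wording of Section 12 as it is.

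**Conclusion.** The point holds as a low-cost improvement. For the post-visit period, the protocol describes only passive, belief-dependent reporting tied to 12 hours, and it leaves open what the 12 hours limits. With waking at 07:00, the window ends before the first night is over for any start earlier than about 14:30 to 15:00. Insomnia is therefore likely to be under-counted, by an amount that varies with the booking time. The statement that most visits are affected rests on assumed start and sleep times; the illustrations run from 56% to 100%.

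The effect is on safety surveillance and on any tolerability statement later made from this trial. As an illustration, zero reports among 112 men on pregnenolone would give an exact two-sided 95% upper limit of 1 − 0.025^(1/112) = 3.2%. That would bound the rate of reported insomnia, not of insomnia itself. The 112 is the planned arm size in Sections 3, 4 and 7; Section 9 expects 36 subjects in total. The plan does not commit to such a statement, and nothing here undermines its stated aims on allopregnanolone levels, attentional bias or depressive symptoms.

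**What to change.** In Section 12, keep the instruction to call and add:
- One short fixed checklist of the acute risks named under Special Precautions: sleep, overstimulation, irritability/anger/anxiety, headache and palpitations. Ask it in identical words in both arms at the end of the visit.
- The same checklist by phone or online form after the first full night.
- A sentence stating that reports are accepted until that contact, which removes the ambiguity about the 12 hours.

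In C.2.7, add a table of the answers by randomised arm at each of the two times.

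The cost is a short wording change to the protocol and consent form, and one brief contact per man by existing staff. More minor events will be recorded. No study procedure or treatment changes.
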